4.6.2 Neutropenia

Patients who have dose-limiting neutropenia despite myeloid growth factor support should have their dose of temozolomide reduced to 75 mg/m^2 (see Appendix IIIB). These patients should continue to receive myeloid growth factor support.

Patients who continue to have dose-limiting neutropenia despite myeloid growth factor support and temozolomide dose reduction are encouraged to undergo bone marrow evaluation to exclude progressive bone marrow metastatic disease. In the absence of progressive bone marrow metastatic disease, these patients should have their dose of MLN8237 reduced by one dose level. These patients should continue to receive myeloid growth factor support. Patients already receiving dose level -1B or an absolute dose of MLN8237 of 10 mg and who require dose reduction will be removed from protocol therapy.

Patients with recurrent dose-limiting neutropenia despite myeloid growth factor support and dose reductions in both MLN8237 and temozolomide will undergo up to one additional dose reduction of MLN8237 and temozolomide in increments of 25% of the starting dose of each agent. Temozolomide will be reduced first followed by MLN8237 in the next cycle if the combination continues to result in dose limiting neutropenia. The dose of temozolomide should be reduced to 50 mg/m²/dose, with dose rounded down to the nearest 5 mg. The dose of MLN8237 should be reduced by an additional dose level. Patients already receiving dose level -1B or an absolute dose of MLN8237 of 10 mg and who require dose reduction will be removed from protocol therapy.

Patients with recurrent dose-limiting neutropenia despite myeloid growth factor support and two dose reductions in both MLN8237 and temozolomide will be removed from protocol therapy.

Patients who are not evaluable for hematologic toxicity due to low counts and bone marrow involvement at study entry should undergo bone marrow re-evaluation if they develop dose-limiting neutropenia. If the bone marrow does not show progressive disease, then the dose modification strategy above should be followed.

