Amendment #5 also changes the dose modification procedures to utilize the existing dose levels rather than using 25% dose reductions. This change will facilitate dose rounding in a more uniform manner based upon the existing protocol dosing nomograms.

Amendment #5 also updates NANT response criteria, including criteria for evaluable disease.

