APPENDIX II. MLN8237 DOSING TABLES FOR PATIENTS RECEIVING ENTERIC COATED TABLETS

Patients receiving the oral solution should have their dose rounded according to section 4.2.1.

(Note that the surface area divisions change at each dose level for rounding purposes)

DOSE LEVEL -1B: 30 MG/M²/DOSE

Body Surface Area (m²)	Dose Level -1 (30 mg/m²)
0.38-0.49	10 mg
0.5-0.83	20 mg
0.84-1.16	30 mg
1.17-1.49	40 mg
1.5-1.83	50 mg
> 1.84	60 mg

DOSE LEVELS 1 AND 1B: 45 MG/M²/DOSE

Body Surface Area (m²)	Dose Level 1 (45 mg/m²)
0.38-0.55	20 mg
0.56-0.77	30 mg
0.78-0.99	40 mg
1.0-1.22	50 mg
1.23-1.44	60 mg
1.45-1.66	70 mg
1.67-1.88	80 mg
> 1.89	90 mg

DOSE LEVEL 2B: 60 MG/M²/DOSE

Body Surface Area (m²)	Dose Level 2 (60 mg/m²)
0.38-0.41	20 mg
0.42-0.58	30 mg
0.59-0.74	40 mg
0.75-0.91	50 mg
0.92-1.08	60 mg
1.09-1.24	70 mg
1.25-1.41	80 mg
1.42-1.58	90 mg
1.59-1.74	100 mg
1.75-1.91	110 mg
> 1.92	120 mg

DOSE LEVEL 3B: 80 MG/M²/DOSE

Body Surface Area (m²)	Dose Level 3 (80 mg/m²)
0.38-0.43	30 mg
0.44-0.56	40 mg
0.57-0.68	50 mg
0.69-0.81	60 mg
0.82-0.93	70 mg
0.94-1.06	80 mg
1.07-1.18	90 mg
1.19-1.31	100 mg
1.32-1.43	110 mg
1.44-1.56	120 mg
1.57-1.68	130 mg
1.69-1.81	140 mg
1.82-1.93	150 mg
> 1.94	160 mg

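### Section 4.6.2 gives two incompatible methods for the second MLN8237 reduction after recurrent dose-limiting neutropenia

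*Combined protocol and SAP*

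**What the plan says.** Section 4.6.2 sets out a ladder for dose-limiting neutropenia that occurs despite growth factor.

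- Temozolomide is lowered first, to 75 mg/m².
- If neutropenia is again dose-limiting and marrow progression is excluded, "these patients should have their dose of MLN8237 reduced by one dose level".
- If it recurs after both drugs have been reduced, each of the two may be lowered once more, "in increments of 25% of the starting dose of each agent". Temozolomide goes first, to 50 mg/m². If dose-limiting neutropenia persists, MLN8237 follows in the next cycle.
- For that MLN8237 step the same paragraph says: "The dose of MLN8237 should be reduced by an additional dose level".
- The paragraph closes with a floor that ends study treatment: "Patients already receiving dose level -1B or an absolute dose of MLN8237 of 10 mg and who require dose reduction will be removed from protocol".

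Two other places bear on this. Section 2.12 says that Amendment 5 "changes the dose modification procedures to utilize the existing dose levels rather than using 25% dose reductions". Section 4.6.1 has the same ladder for thrombocytopenia, and its corresponding sentence has no percentage clause.

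**The concern.** One MLN8237 step is sized in two ways within one paragraph of current operative text. The percentage clause cannot be confined to temozolomide, because its sentence names both drugs and refers to each agent. Sections 4.6.1 and 4.6.3 to 4.6.6 apply no percentage to MLN8237; the 25% steps in 4.6.4 are for irinotecan.

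Sites could handle the same toxicity differently. Section 4.5 sends patients with dose-limiting toxicity to section 4.6, so this paragraph helps decide who stays on treatment and at what dose. Number of courses and reason off treatment are outcomes to be reported under section 10.6. The oral solution is dosed by calculation and rounded down to the nearest 0.5 mg (section 4.2.1), so no tablet table would stop a site from preparing an intermediate dose.

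**Working it through.** **Inputs.** The MLN8237 dose levels are 30 ("DOSE LEVEL -1B: 30 MG/M²/DOSE"), 45 ("DOSE LEVELS 1 AND 1B: 45 MG/M²/DOSE"), 60 (2B) and 80 mg/m² (3B), from Appendix II and section 4.3. Phase 2 starts at 60 and the oral-solution cohort starts at 45 (sections 2.12 and 4.3). Level 3B was used only in the completed phase 1 portion.

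**Check on temozolomide.** 25% of 100 is 25, so the steps are 100 − 25 = 75 and 75 − 25 = 50 mg/m². These are the doses the section states, so the percentage clause causes no conflict for temozolomide.

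**MLN8237.** The first reduction is one dose level for everyone. For the second reduction:

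- Dose-level method: go down one more level; if already at -1B, the patient is removed.
- Percentage method: subtract 0.25 × starting dose from the current dose. An alternative reading takes two 25% increments off the starting dose, leaving 0.50 × start.

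| Start (mg/m²) | After first reduction | Second, by dose level | Second, by 25% clause |
|---|---|---|---|
| 60 | 45 | 30 | 45 − 15 = 30; or 0.50 × 60 = 30 |
| 80 | 60 | 45 | 60 − 20 = 40; or 0.50 × 80 = 40 |
| 45 | 30 (-1B) | removal | 30 − 11.25 = 18.75; or 0.50 × 45 = 22.5 |

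A patient starting at 30 mg/m² is already at -1B and is removed when the first MLN8237 reduction is required, so the second step does not arise. Appendix II has no dosing table for 40, 22.5 or 18.75 mg/m².

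**Who could reach the disputed step.** Section 10.5 allows up to 6 evaluable patients at level 1B, and up to 6 more at the MTD if further pharmacokinetic data are needed. If 1B is the MTD, that is 6 + 6 = 12, replacements aside. Section 4.2 provides for phase 1 patients who remain on therapy but does not say how many. Those who started at 45 or 80 mg/m² would be added.

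**When it is reached.** Four dose-limiting episodes lead to it: temozolomide to 75, MLN8237 down one level, temozolomide to 50, and then the second MLN8237 reduction. Under section 4.4, neutropenia is dose-limiting only if the neutrophil criterion for the next cycle is not met by day 36.

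**The case against.** The strongest reply is that the paragraph settles the 45 mg/m² case itself. The removal sentence does not depend on how a reduction is sized. A patient who started at 45 is at -1B after the first step, so needing any further MLN8237 reduction triggers removal. If every sentence is applied together, no starting dose in the open cohorts has two outcomes. Largely, this stands. Continued dosing at 18.75 or 22.5 mg/m² requires a site to let the percentage clause override the removal sentence, so the two outcomes are not equally supported. The reply does not cover a start at 80 mg/m²: after the first step that patient is at 60, the floor does not apply, and 45 and 40 both remain on the page.

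A second reply is that section 2.12 shows what Amendment 5 intended. A reader may well conclude that the percentage clause survived from before that amendment. But a rationale section is a poor place for a site to look for a dose or removal instruction, and section 4.6.2 still contradicts itself.

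Three stronger readings are tempting, and the documents do not support them:

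- A reader might infer that the methods diverge from the first MLN8237 reduction. They do not: that reduction is by dose level only, and the percentage clause is confined to the additional one.
- A reader might take all of the oral-solution cohort to be exposed. The maximum of 18 in section 10.1 covers every dose level. Patients assigned 2B get the same doses under both methods, and those assigned -1B are removed at the first MLN8237 reduction.
- A reader might infer damage to a primary result. The oral-solution primary endpoint is first-cycle toxicity (section 10.3), which comes before any of these steps. Phase 2 response patients start at 60 mg/m², where the methods agree.

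**Conclusion.** The point holds in limited form. Section 4.6.2 states two incompatible methods for the second MLN8237 reduction, and one of them disagrees with section 2.12 and has no counterpart in 4.6.1. The consequence is nil from 60 mg/m² and 45 versus 40 from 80 mg/m². From 45 mg/m² it is removal, with a risk that a site instead calculates 18.75 or 22.5. The 45 mg/m² ambiguity concerns about 6 to 12 oral-solution patients starting at 1B, plus any phase 1 patients who started at 45 and are still on treatment. Few of them are likely to reach the step.

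This rests on three assumptions: both MLN8237 reductions are made under 4.6.2, with none made earlier for another toxicity; 1B is the MTD for the oral solution if 12 is to be reached; and the phase 2 starting dose stays at 2B (a toxicity review under section 10.4 could lower it for new patients). It should be corrected because it is a dosing instruction, not because it threatens a trial conclusion.

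**What to change.** Reconcile the percentage clause and the dose-level sentence in section 4.6.2 with each other, with the removal sentence in the same paragraph, with section 4.6.1 and with the Amendment 5 rationale, so that one reduction method is stated for MLN8237. If neutropenia is meant to differ from thrombocytopenia, say so and why. Which method is clinically right is for the clinical team to decide. The cost is a wording change in the next amendment; no sample size, endpoint or analysis changes. Until then, a clarification to sites with phase 1 or oral-solution patients on therapy would keep handling uniform.

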4.6.3 Mucositis

Patients who develop dose-limiting mucositis (per section 4.4) should have their dose of MLN8237 reduced by one dose level with their next cycle of therapy. Patients already receiving dose level -1B or an absolute dose of MLN8237 of 10 mg and who require dose reduction will be removed from protocol therapy.

Patients who continue to have dose-limiting mucositis despite initial MLN8237 dose reduction should have their dose of MLN8237 reduced by another dose level. Patients already receiving dose level -1B or an absolute dose of MLN8237 of 10 mg and who require dose reduction will be removed from protocol therapy.

If mucositis remains dose-limiting despite two MLN8237 dose reductions, temozolomide should be reduced to 75 mg/m² (see Appendix IIIB). Patients with recurrent dose-limiting mucositis despite these dose reductions should be removed from protocol therapy.

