3.2.11 Body Surface Area

Due to the size of MLN8237 tablets, patients must be at least 0.38 m^2 to be eligible for the phase 2 portion of the study. There is no BSA limit for patients participating in the oral solution cohort.

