4.2.1 MLN8237

MLN8237 will be given once daily by mouth on days 1-7 of each 21-day cycle. On days 1-5, the dose should be given one hour prior to the start of the irinotecan infusion and at the same time as the dose of temozolomide on those days.

For patients in the phase 2 portion, the dose of MLN8237 will be 60 mg/m^2 (dose level 2B) using exclusively the enteric coated tablet. The dose should be rounded to the nearest 10 mg using the dosing table in Appendix II, with doses capped at 2 m^2 . Tablets should not be crushed, split, or chewed. The dose can be taken either on an empty stomach or with food on Days 6 and 7, though on Days 1-5 should be taken without food as the dose is taken at the same time as temozolomide (see below). If a patient vomits after taking a dose, it should not be re-dosed.

For patients in the oral solution cohort, the dose of MLN8237 will be based upon the dose level assigned at study entry. The oral solution may be administered by mouth, via nasogastric tube, or via gastrostomy tube. The calculated dose should be rounded down to the nearest 0.5 mg (0.1 mL of the 5 mg/mL oral solution). The dose must be taken on an empty stomach (NPO two hours before and one hour after each dose). If a patient vomits after taking a dose, it should not be re-dosed.

EXAMPLES

- Assigned dose 45 mg/m^2 and BSA 0.83 m^2 → Calculated dose = 37.35 mg → Round down to 37.0 mg → Administer 7.4 mL of 5 mg/mL solution
- Assigned dose 45 mg/m^2 and BSA 0.84 m^2 → Calculated dose = 37.8 mg → Round down to 37.5 mg → Administer 7.5 mL of 5 mg/mL solution

For both formulations of the drug, systemic antacids (both H2 receptor antagonists and proton pump inhibitors) may alter MLN8237 exposure and should be avoided during MLN8237 treatment. Locally-acting antacids should not be taken simultaneously with MLN8237 but antacids can be given up to 2 hours prior or 2 hours following MLN8237 administration.

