4.6 Dose Modification

4.6.1 Thrombocytopenia

Patients evaluable for hematologic toxicity who develop dose-limiting thrombocytopenia (per section 4.4) should have their dose of temozolomide reduced to 75 mg/m^2 (see Appendix IIIB).

Patients who continue to have dose-limiting thrombocytopenia despite temozolomide dose reduction should have a bone marrow evaluation to exclude progressive bone marrow metastatic disease. In the absence of progressive bone marrow disease, these patients should have their dose of MLN8237 reduced by one dose level. Patients already receiving dose level -1B or an absolute dose of MLN8237 of 10 mg and who require dose reduction will be removed from protocol therapy.

Patients with recurrent dose-limiting thrombocytopenia despite dose reductions in both MLN8237 and temozolomide will undergo up to one additional dose reduction of MLN8237 and temozolomide. Temozolomide will be reduced first followed by MLN8237 in the next cycle if the combination continues to result in dose limiting thrombocytopenia. The dose of temozolomide should be reduced to $50 \text{ mg/m}^2/\text{dose}$, with dose rounded down to the nearest 5 mg. The dose of MLN8237 should be reduced by an additional dose level. Patients already receiving dose level -1B or an absolute dose of MLN8237 of 10 mg and who require dose reduction will be removed from protocol therapy.

Patients with recurrent dose-limiting thrombocytopenia despite two dose reductions in both MLN8237 and temozolomide will be removed from protocol therapy.

Patients who are not evaluable for hematologic toxicity due to low counts and bone marrow involvement at study entry who develop dose limiting thrombocytopenia should undergo bone marrow re-evaluation. If the bone marrow does not show progressive disease, then the dose modification strategy above should be followed.

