4.6.4 Diarrhea

In addition to oral cephalosporin prophylaxis, other guidelines for patients with dose-limiting diarrhea include consideration of the possibility of cholinergic syndrome if diarrhea occurs within hours of the irinotecan infusion. Patients with early diarrhea may benefit from pretreatment with atropine (0.01 mg/kg IV; max dose 0.4 mg), as well as prolonging the irinotecan infusion to 90 minutes. Additional strategies for treating patients with therapy-associated diarrhea are given in section 5.5.

Patients who continue to have dose-limiting diarrhea despite cephalosporin prophylaxis and other measures above should have the dose of irinotecan reduced by 25% to 37.5 mg/m²/dose. These patients should continue to receive the above supportive therapies with subsequent cycles.

Patients with recurrent dose-limiting diarrhea despite supportive measures and irinotecan dose reduction should have the dose of irinotecan reduced by another 25% of the initial starting dose to 25 mg/m²/dose.

If diarrhea remains dose-limiting despite two irinotecan dose reductions, MLN8237 should be reduced by one dose level. Patients already receiving dose level -1B or an absolute dose of MLN8237 of 10 mg and who require dose reduction will be removed from protocol therapy. Patients with recurrent dose-limiting diarrhea despite these dose reductions should be removed from protocol therapy.

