4.6.5 Mood alterations

Patients who develop dose-limiting mood alteration while receiving MLN8237 should have the remainder of the MLN8237 for that cycle held. These patients should have their dose of MLN8237 reduced one dose level with their next cycle of therapy. Patients already receiving dose level -1B or an absolute dose of MLN8237 of 10 mg and who require dose reduction will be removed from protocol therapy.

Patients with recurrent dose-limiting mood alteration despite initial MLN8237 dose reduction should have their dose of MLN8237 reduced by another dose level. Patients already receiving dose level -1B or an absolute dose of MLN8237 of 10 mg and who require dose reduction will be removed from protocol therapy.

Patients with recurrent dose-limiting mood alteration despite these dose reductions will be removed from protocol therapy.

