4.6.6 Other toxicities

Patients who develop other dose-limiting non-hematologic toxicities (per section 4.4) should have their dose of MLN8237 reduced by one dose level. Patients already receiving dose level -1B or an absolute dose of MLN8237 of 10 mg and who require dose reduction will be removed from protocol therapy.

Patients with recurrent dose-limiting toxicity despite initial MLN8237 dose reduction should have their dose of MLN8237 reduced by another dose level. Patients already receiving dose level -1B or an absolute dose of MLN8237 of 10 mg and who require dose reduction will be removed from protocol therapy.

Patients with recurrent dose-limiting toxicity despite these dose reductions will be removed from protocol therapy.

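### In three narrow BSA bands, the one-level MLN8237 reduction after a DLT leaves the tablet dose unchanged

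*Combined protocol and SAP*

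**What the plan says.** The MLN8237 reduction is defined by dose level throughout section 4.6, but it comes at a different point for each toxicity.

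- Mucositis (4.6.3): it is the first response. Patients "should have their dose of MLN8237 reduced by one dose level with their next cycle of therapy".
- Other non-hematologic toxicity (4.6.6): it is again the first response. "Patients who develop other dose-limiting non-hematologic toxicities (per section 4.4) should have their dose of MLN8237 reduced by one dose level".
- Mood alteration (4.6.5): MLN8237 is held for the rest of the cycle, and then "These patients should have their dose of MLN8237 reduced one dose level with their next cycle of therapy".
- Thrombocytopenia (4.6.1): temozolomide is cut to 75 mg/m² first. If the DLT persists, "In the absence of progressive bone marrow disease, these patients should have their dose of MLN8237 reduced by one dose level". Section 4.6.2 follows the same order for neutropenia.
- Diarrhea (4.6.4): it comes last. "If diarrhea remains dose-limiting despite two irinotecan dose reductions, MLN8237 should be reduced by one dose level". A further dose-limiting episode leads to removal.

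Each subsection carries the same stopping rule: "Patients already receiving dose level -1B or an absolute dose of MLN8237 of 10 mg and who require dose reduction will be removed".

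On tablet doses, section 4.2.1 states "The dose should be rounded to the nearest 10 mg using the dosing table in Appendix II", and the tablets may not be split. Section 3.2.11 sets the phase 2 size limit: "Due to the size of MLN8237 tablets, patients must be at least" 0.38 m². Section 2.12 records that Amendment 5 replaced 25% cuts with the existing levels so that rounding would follow the nomograms.

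**The concern.** A reduction after a DLT is meant to lower exposure to the drug. Levels 2B, 1B and -1B are 60, 45 and 30 mg/m², so at low BSA the gap between adjacent levels is less than one 10 mg tablet, and both levels can round to the same number of tablets. The level on the record then changes while the dose does not. For mucositis and other non-hematologic DLTs, where this is the first protective step, the child would go back to the same MLN8237 dose. For diarrhea it would be the only MLN8237 reduction available before removal.

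**Working it through.** **Inputs.** Appendix II tables for levels 2B, 1B and -1B; the nearest-10-mg rule in 4.2.1; the BSA minimum of 0.38 m² in 3.2.11; the step and removal rules in 4.6.

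**1. Reproduce the tables.** Level (mg/m²) × BSA, rounded to the nearest 10 mg with halves up, was compared with Appendix II at every 0.01 m² from 0.38 to 2.00. It agrees at every entry for every level. Examples at 0.41 m²: 60 × 0.41 = 24.6, which rounds to 20 mg; 45 × 0.41 = 18.45, which also rounds to 20 mg. The tables contain no error.

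**2. Compare adjacent levels.**

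| BSA (m²) | 2B (mg) | 1B (mg) | -1B (mg) | Step with no change |
|---|---|---|---|---|
| 0.38-0.41 | 20 | 20 | 10 | 2B to 1B |
| 0.42-0.49 | 30 | 20 | 10 | none |
| 0.50-0.55 | 30 | 20 | 20 | 1B to -1B |
| 0.56-0.58 | 30 | 30 | 20 | 2B to 1B |
| 0.59-0.74 | 40 | 30 | 20 | none |

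Neither step has a tie above 0.58 m². The 2B dose never equals the -1B dose. The oral solution, rounded down to 0.5 mg, has no tie at BSA 0.15-2.00 m².

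**3. Check the removal rule.** When the empty step is made, these children are at 2B or 1B and take 20 or 30 mg. They are neither at -1B nor at 10 mg, so the rule does not apply.

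**4. Size, as dose per m² before and after the step.**

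- 0.38-0.41 m²: 20/0.41 = 48.8 to 20/0.38 = 52.6 mg/m². Against 45: 48.8/45 = 1.08 and 52.6/45 = 1.17, so 8-17% above level 1B.
- 0.56-0.58 m²: 30/0.58 = 51.7 to 30/0.56 = 53.6 mg/m². Against 45: 1.15 and 1.19, so 15-19% above level 1B.
- 0.50-0.55 m²: 20/0.55 = 36.4 to 20/0.50 = 40.0 mg/m². Against 30: 1.21 and 1.33, so 21-33% above level -1B.

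**5. The same doses against the level being left.** For 2B, 48.8/60 = 0.81 up to 53.6/60 = 0.89. For 1B, 36.4/45 = 0.81 up to 40.0/45 = 0.89. Rounding had already put these children 11-19% below the nominal dose.

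**6. Growth between cycles.** Section 4.2 recalculates doses from height and weight before each cycle, so the bands hold for a fixed BSA. A child with a DLT on 30 mg at 2B and BSA 0.58 m², who measures 0.59 m² at the next cycle, is given 30 mg at 1B.

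**The case against.** The best defence is that rounding had already done the work. A child at 0.38-0.41 m² was taking the tabulated 1B dose all along, and Amendment 5 deliberately tied reductions to the nomograms. Removing a tablet also overshoots: 10 mg at 0.38-0.41 m² is 42-46% below 45 mg/m², whereas the present dose is 8-17% above it. At 0.56-0.58 m², 20 mg is 21-23% below, against 15-19% above now. This stands as a trade-off, and it makes the excess over nominal smaller than a full step. It does not answer the point, because the child had the toxicity at the dose actually taken.

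Other safeguards exist but do not supply a lower dose. DLTs go immediately to the study chair (4.4), continuing after a DLT is optional (4.5), and a physician may stop therapy (9.1). The 25% wording left in 4.6.2 concerns only the additional reduction, and only for neutropenia.

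A reader might infer more than the documents support:

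- **That every DLT leads straight to an empty step.** It does not. Hematologic DLT and diarrhea reach the MLN8237 step only after temozolomide or irinotecan cuts, and mood alteration only after a hold.
- **That these children can never be reduced.** Two successive level steps always lower the dose.
- **That an empty step certainly uses up a permitted reduction.** This is the literal reading, but an unchanged dose is arguably not a reduction. The text does not settle it.
- **That temozolomide has a parallel gap below 0.5 m²,** because the second reduction has no mg/kg figure. The stated 50 mg/m² can be applied at any BSA, so no child is left without a dose.

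**Conclusion.** The point holds as a gap between the one-level rule and whole-tablet rounding. The change in MLN8237 dose is 0 mg for 2B to 1B at 0.38-0.41 and 0.56-0.58 m², and for 1B to -1B at 0.50-0.55 m². This is an exact table look-up and needs no assumption beyond a BSA that stays the same from one cycle to the next.

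Its reach is small. The documents give no BSA distribution. Phase 2 takes 14-20 patients, who must swallow whole tablets, and the child must also have a DLT that leads to this step. The number affected may be zero.

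A reader might infer that the trial's conclusions are at risk, but the documents do not support that. The phase 2 toxicity triggers in 10.4 count first-course DLTs, and evaluability for response in 10.2.2 rests on cycle 1 dosing; both come before any reduction. Dose escalation is now confined to the oral solution cohort, which has no ties. The matter is one of patient protection and clear instructions to sites, and is minor.

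**What to change.** Add to section 4.6, with a note in Appendix II: if the next lower level gives the tablet dose the patient is already taking, lower the dose by one 10 mg tablet from the dose actually taken, and count this as a single one-level reduction. The patient is not treated as being at -1B for the removal rule unless -1B is the level assigned.

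The first reduction from 2B then gives 10 mg at 0.38-0.41 m² and 20 mg at 0.56-0.58 m². For the second reduction at 0.50-0.55 and 0.56-0.58 m², where the child takes 20 mg and -1B is also 20 mg, the sponsor should state either 10 mg or removal. Comparing with the dose actually taken also covers growth between cycles. A jump to the next level that lowers the dose would be worse: it puts the child at 0.56-0.58 m² at -1B, so the next MLN8237 reduction would mean removal.

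Costs to accept:

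- 10 mg is 24.4-26.3 mg/m² at 0.38-0.41 (10/0.41 to 10/0.38), 18.2-20.0 at 0.50-0.55 (10/0.55 to 10/0.50) and 17.2-17.9 at 0.56-0.58 (10/0.58 to 10/0.56). All are below the nominal 30 mg/m² of -1B.
- A child at 0.38-0.41 m² reaches the 10 mg removal floor after one reduction. For mucositis, that child would be removed before the second MLN8237 step and before the temozolomide step in 4.6.3.

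The text change fits a minor amendment; the dose values are for the sponsor to set.
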